NIAID	National Institute of Allergy and Infectious Diseases
NIH	National Institutes of Health
PBMC	Peripheral Blood Mononuclear Cells
PD ₂₀	Provocative Dose that causes a 20% fall in FEV ₁
PI	[Site] Principal Investigator
RNA	Ribonucleic Acid
SACCC	Statistical and Clinical Coordinating Center
SAE	Serious Adverse Event/Serious Adverse Experience

Protocol Summary

Full Title:	Urban Environment and Childhood Asthma
Short Title:	URECA
Conducted by:	National Institute of Allergy and Infectious Diseases
Principal Investigator:	[name]
Sample Size:	N=609 originally enrolled
Study Population:	Inner-city children at high risk for development of asthma due to family history, plus a small sample of inner-city children without family history.
Accrual Period:	N/A – Study participants were accrued from 2005-2007
Study Design:	URECA is a longitudinal birth cohort study which is being extended to follow study children to age 17 years.
Study Duration:	Start Date: 1 April 2021 End Date: 31 December 2024
Primary Objective:	To determine the wheezing, asthma and atopy phenotypes in minority children growing up in poor urban neighborhoods as they develop from birth through adolescence.
Secondary Objectives:	
1. To longitudinally analyze the development of lung function and its relationship to asthma.2. To identify which urban exposures (allergens, pollutants, microbes, viral infections, stress) from early life onward affect the development and natural history through adolescence of asthma, allergic rhinitis and allergic sensitization.3. To determine the association of pre-pubertal obesity and the effect of pubertal changes in adiposity and sex hormones on lung growth and asthma onset, prevalence and morbidity.

Exploratory Objectives:

1. To provide samples for analysis and outcomes data for use in mechanistic studies to understand relationships between environmental exposures, changes in immune development, alterations in DNA methylation patterns of airway cells, and the development of allergic sensitization, allergic rhinitis and asthma.
2. To work collaboratively with investigators outside of the NIAID asthma network on mechanistic or clinical studies to test novel hypotheses and to validate, compare and contrast findings from URECA with those in other cohorts or clinical studies.

Endpoints:

Incidence and prevalence of asthma and occurrence of specific phenotypes of asthma

Schematic of Study Design

[figure not shown]

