10.4.2 Analysis of Secondary Objectives

10.4.2.1 Early life exposure to household allergens

To determine whether early life exposure to allergens in the home in the absence of a diverse microbiome is associated with sensitization to those allergens and respiratory symptoms (perennial rhinitis and allergic asthma phenotypes), we will examine the association between early-life exposures to allergens and diversity in the microbiome towards allergic sensitization. The assumption is that children with high levels of exposure and low microbiome diversity will have a higher likelihood of early sensitizations. Early sensitizations will be obtained by latent class mixed model analysis combining both skin tests and specific IgEs to aeroallergens. Then a multinomial logit model, with possible adjustments for race and gender, will test the (multiplicative & additive) interaction between these two predictors and the likelihood of early sensitization. Furthermore, these prolonged exposures can have a compound effect in sensitization, and summary measures such as cumulative exposures may not fully capture these relationships. We proposed to extend the model suggested above by using a distributed lag linear (and non-linear) model with flexible exposure-response and lag-response functions to examine the association between sensitization and exposures in early life.

Pathway analysis will be used to determine how a host of environmental factors contribute to the development of rhinitis with specific classifications. Based on medical evidence in the

published literature we will develop and test a conceptual model to describe how different risk factors domains (i.e. allergic inflammation, pulmonary physiology, environmental exposures, etc.) are linked to rhinitis. A causal network analysis will be implemented using structural equations models to simultaneously perform (1) a confirmatory factor analysis in each domain to estimate the relationship between the domain of interest and each observed variable used to measure the domain and (2) a series of regression models to estimate the standardized direct effect of each independent domain onto rhinitis.

10.4.2.2 Effect of pubertal changes in adiposity and sex hormones on lung growth and asthma onset, prevalence and morbidity

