Levels of steroid hormones, steroid binding proteins, leptin, adiponectin and serum inflammatory indicators (IL-6, TNF- α , CRP) at 8, 10, 12, 14/15, and 16/17 years of age will be compared to asthma status by ANOVA. These analyses will also be stratified by sex, and we will test whether sex hormones and sex hormone binding proteins modify the relationship between leptin and asthma prevalence in post-pubertal girls and boys. Body habitus and measurements of fitness (6-minute walk in clinic) will also be compared among children with vs. without asthma. We expect that children at greatest risk for asthma will be those with low fitness and activity, high BMI, increased serum inflammatory markers, and atopy.

We will use trajectory analysis to examine whether changes in weight or BMI are related to asthma prevalence in children from age 10 to 17 years. We will use semiparametric mixture modeling—which combines latent growth curve and mixture modeling—to identify growth trajectories over time separately for boys and girls. Trajectory parameters will be estimated using the maximum likelihood approach built upon a binary logit model, using the BIC (Bayesian information criterion) to identify the best model. The objective of model selection is to summarize the distinctive features as parsimoniously as possible. The resulting growth trajectories will be used as predictor variables in a logistic regression model predicting development of asthma. The model will be tested for effect modification by sex.

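### The BMI trajectory model in section 10.4.2.2 is valid as an association with asthma prevalence but does not address asthma onset, and its test of effect modification by sex is estimable only if boys' and girls' classes are matched or common

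*Protocol*

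**What the plan says.** The last paragraph of Protocol section 10.4.2.2 sets the question as "whether changes in weight or BMI are related to asthma prevalence in children from age 10 to 17 years". Semiparametric mixture models, with BIC for model choice, are to "identify growth trajectories over time separately for boys and girls". The paragraph then says: "The resulting growth trajectories will be used as predictor variables in a logistic regression model predicting development of asthma". It ends: "The model will be tested for effect modification by sex".

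The first paragraph of the section works by current status. Hormones, adipokines and inflammatory markers at several ages "will be compared to asthma status by ANOVA", the leptin question concerns prevalence, and body habitus and fitness are compared between children with and without asthma.

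The section heading is "Effect of pubertal changes in adiposity and sex hormones on lung growth and asthma onset, prevalence and morbidity", which matches secondary objective 2 in section 2.2. The Protocol Summary gives the endpoints as "Incidence and prevalence of asthma and occurrence of specific phenotypes of asthma". Section 3.2.1 reports that 29% met the asthma definition at age 7. Section 1.1 has follow-up running into the 17th year, and section 10.5 gives 442 of 609 children retained.

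**The concern.** Onset and prevalence are listed as different targets, yet one paragraph moves from one to the other with the same predictor and no change of risk set or time window. Objective 2 asks for the effect of pubertal change in adiposity on onset, and this is the only model in the section that could be taken to answer it. If a class with rising BMI shows more asthma, three explanations remain open: BMI rose before onset, BMI rose after onset, or the asthma predates the window. The fitted model cannot tell them apart.

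The sex test raises a separate problem. A class found among girls and a class found among boys are different categories unless something ties them together, and the section states nothing that does.

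**Working it through.** **The Protocol's own figure.** 442/609 = 72.6%, which rounds to the stated 73%. The Protocol gives no power or event calculation for this analysis.

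**What the onset outcome could mean.**

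1. *Having met the definition by some age*, as section 3.2.1 uses the term for age 7. Cases before age 10 may then count. If 29% holds among the 442 (an assumption), 0.29 × 442 = 128 children had asthma by age 7 and 442 − 128 = 314 did not. The share of cases that predate the window is

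   442·prev·(1−rem) / [442·prev·(1−rem) + 442·(1−prev)·inc]

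   The ranges assumed here, not given in the Protocol, are prevalence at entry 20–29%, new onset 5–20% and remission 0–30%. The lowest share is 61.9/(61.9 + 70.7) = 47%; the highest is 128.2/(128.2 + 15.7) = 89%. This is a prevalence model, and the section then contains no onset analysis.

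2. *New asthma during the window.* Reading 10–17 as the BMI window, with yearly values (8) and onset equally likely in each of 7 intervals, a new case has 7, 6, …, 1 values after onset. The mean is 4 of 8, or 50%. With four visits (10, 12, 14/15, 16/17) the counts are 3, 2, 1 of 4, mean 2 of 4, again 50%. Follow-up ends where the trajectory ends, so no later outcome period exists.

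**Illustration that direction is not separated.** All inputs are assumed, and BMI never causes asthma.

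- n = 442, 29% with asthma before the window, 10–20% new onset, top third of BMI slope as the rising class, 1000 runs per setting. If BMI rises by 0.03–0.10 SD per year only after onset, the model on all children rejects in 46–100% of runs. Dropping only the pre-window cases still gives 12–75%. Trajectory at 10–13 and onset at 13–17, among children free of asthma at 13, gives 4.4–4.7%. With no post-onset rise, the first two versions reject in 4–6%.
- n = 314, three fitted mixture classes, a step in BMI after onset. For −0.2, 0 and +0.2 z, the odds ratio of the highest class is 0.81–0.87, 0.98–1.12 and 1.17–1.28, with rejection of 7–12%, 4–9% and 5–13%.

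The two designs give very different sizes, and the sign follows the assumed shift. They show that the model does not identify direction; they do not estimate a bias for this cohort.

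**Sex test.** Take three classes per sex.

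- Six sex-specific labels: the design matrix has rank 6, and stays at rank 6 when sex and class-by-sex are added. Interaction degrees of freedom: 6 − 6 = 0. The same holds for 3 and 4 classes (rank 7 throughout) and for 2 and 3 (rank 5 throughout).
- Matched or common labels: main effects have rank 1 + 2 + 1 = 4, and rank 6 with the interaction. Degrees of freedom: 6 − 4 = 2.

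In simulations with the same true structure and 221 children per sex, separate BIC selection gave unequal class counts in 1% of runs in three setups and 36% in a fourth. Failure to match is therefore possible, not shown.

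**The case against.** **The Protocol does not say that BMI change precedes onset.** This is correct. A reader might infer such a claim from the prediction wording and from the word effect in objective 2, but the stated question is one of relation to prevalence. Prevalence is a named target, and the analysis serves it validly. A charge that the trajectory analysis as a whole is invalid is not supported. What stands is that onset is also named, and nothing in 10.4.2.2 addresses it.

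**The age range might describe only prevalence, not the BMI window.** This is possible. Ages 10–17 is the natural reading, and no other window is given. The 50% count depends on it, on onset meaning new asthma, and on uniform onset.

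**The statistical analysis plan may settle the risk set, lag and matching.** It may, and quarterly calls with records from birth would allow it. But the Protocol already pairs a prevalence question with a regression on development of asthma, and separate classes with a sex interaction. The plan would have to reinterpret that text. Section 10.4.3 shows that the Protocol can separate predictor from outcome in time: there, apart from demographics, early-life predictors come from the first three years.

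**The simulated odds ratios are not evidence about this cohort.** Agreed. The post-onset shifts are invented, and with none there is essentially no bias. A reader might infer that the planned result will be biased upward by a stated amount; the documents give no basis for a direction or a size.

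**Separate trajectories by sex are sensible in puberty.** Also agreed. A reader might conclude that the sex test is impossible. It is not: matching restores it, and the section does not forbid matching.

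**Conclusion.** The point holds in limited form. The whole-window trajectory analysis can be reported as an association with asthma prevalence. It does not address onset under either reading: pre-window cases may count (47–89% of cases under the assumed ranges), or about half of a new case's BMI values come after onset (yearly visits, uniform onset, 10–17 as the BMI window). The direction and size of any resulting bias are unknown. The limit lies in the written model, not in the data, which could support an onset analysis.

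The sex point needs no simulation. The interaction has 0 degrees of freedom with sex-specific labels and 2 with three matched or common classes, so the test as described is incomplete until one of these is chosen. The matter concerns a secondary objective of an observational cohort and merits an amendment to the wording.

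**What to change.** Amend the last paragraph of 10.4.2.2:

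- **(a) Prevalence.** Keep the whole-window trajectory classes against asthma prevalence and report them as association only.
- **(b) Onset.** Add an analysis in children without asthma at the start of follow-up, using only BMI level and BMI change measured before the onset interval. Use either a discrete-time logistic model with lagged level and change, or a landmark model. Change must be included, because a lagged level alone does not test pubertal change.
- **(c) Sex.** Match the sex-specific classes by a pre-stated rule, or derive common classes on age- and sex-standardised BMI, or drop the interaction test. Label any sex interaction exploratory. Common classes assume shared z-score shapes in both sexes.

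Nothing in conduct or data collection changes. The cost is precision. The table assumes 314 children at risk, 80% power and two-sided 5%. The approximate detectable odds ratio per SD is exp(2.802·SE), with SE = 1/√(n·p·(1−p)). The landmark is at age 13 with uniform onset, so 4/7 of events remain.

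| Assumed incidence | Lagged: events | Lagged: SE | Lagged: OR | Landmark: events | Landmark: OR |
|---|---|---|---|---|---|
| 5% | 16 | 0.259 | 2.1 | 9 | 2.6 |
| 10% | 31 | 0.188 | 1.7 | 18 | 2.0 |
| 20% | 63 | 0.141 | 1.5 | 36 | 1.6 |

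For the lagged model, the detectable ratio of odds ratios between the sexes (SE doubled) is about 4.3, 2.9 or 2.2, which is why the interaction should be exploratory. All figures are before further attrition. If only 20% had asthma at entry, 354 children would be at risk.

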10.4.3 Analysis of Exploratory Endpoints

The overall approach to identify phenotypes will be similar to that used with the 7-year and 10-year data sets, using latent class mixed models to identify homogenous subpopulations within sets of longitudinal variable trajectories. Variables characterizing the trajectory clusters (e.g. symptoms, allergic sensitization, lung function and BMI) and other relevant predictors (including demographics) will be used to represent subjects in a Gower distance matrix, which can handle mixed data types. The Akaike information criterion will be used to select the number of clusters (i.e. number of subpopulations) for each variable. These variables will be evaluated for collinearity and variable sets that are highly collinear will be represented by a constituent variable that is most representative of each subset. Children will be clustered to identify distinct phenotypes selected using four criteria: 1) a generalization of the within-clusters sum of squares measure, 2) average silhouette width, 3) Dunn index, and 4) the ratio of average-within versus average-between clusters. In this aim, we will identify asthma endotypes by linking respiratory allergy and asthma phenotypes to mechanistic data, including the patterns of airway epithelial cell DNA methylation and gene expression at 11 and 15 years that will be calculated in Aim 1. Our approach will first assign each subject to one of the phenotypes defined by the approach for Subaim 3.1. We will then conduct an analysis to identify gene expression patterns and

methylation patterns (from ages 11 and 15), and environmental exposures that are characteristic of each phenotype and distinguish among them.

To identify endotypes, we will use a sparse multinomial logistic regression model. Variables for these models include the DNA methylation and expression modules (Aim 1), and environmental exposures (e.g. viral infections, allergens, microbes, tobacco smoke). Thus, the model will represent endotypes by mapping from biological states and environmental exposures to clinical phenotypes. In a sparse model, the learning algorithm is biased towards selecting a relatively small number of variables. Thus, although we will include a moderately large number of candidate variables in the models, only a sufficient number of variables to distinguish the phenotypes are selected. We will use well established sparse learning methods, such as LASSO and elastic net, which are well suited to high-dimensional data sets that include many potentially irrelevant variables.

We will next identify biomarkers for predicting respiratory allergy and asthma phenotypes that we observe at ages 11 and 15. This analysis will start with subjects clustered according to the phenotypes that we defined in Aim 3.1 and will proceed by inferring functions composed from individual early-life biomarkers that are predictive of the phenotype an individual subject will exhibit. Sparse multinomial logistic regression models will be used to evaluate early life biomarkers. The candidate predictor variables for these models will include (i) demographics, (ii) clinical variables such as wheeze frequency, (iii) gene expression measurements from nasal epithelial cells, and (iv) DNAm measurements from nasal epithelial cells. Aside from demographics, these variables will come from measurements taken during the first three years of life.

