Aim 2 will test the hypothesis that early life exposure to allergens in the home in the absence of a diverse microbiome is associated with sensitization to those allergens and respiratory symptoms (perennial rhinitis and allergic asthma phenotypes). We will identify additional early life exposures that are associated with no sensitization, sensitization without clinical symptoms and sensitization with respiratory symptoms.

Aim 3 will integrate the diverse data available in URECA children to identify asthma endotypes and their predictors by: **a**) using advanced clustering techniques to identify respiratory and asthma phenotypes from longitudinal data, including upper and lower airway symptoms, allergic sensitization, lung function, BMI and psychosocial factors such as depression and risky behaviors; **b**) linking phenotypes to potential causative factors, such as specific environmental exposures (home microbiome and allergen exposure), AEC DNAm and gene expression patterns, upper airway microbial colonization, and serum hormone levels (e.g. insulin, sex hormones, adipokines); and **c**) identifying biomarkers to enable early identification of asthma endotypes.

[figure not shown]

Figure 2. Specific aims (numbered).

The results of these studies will link the pivotal early life exposures to airway epithelial cell DNAm and gene expression patterns, and ultimately to clinical expression of allergic diseases and asthma. These integrated data can be used to detect at-risk children at an early age, and from these pathways, develop and test interventions in early life to prevent allergy and asthma in urban children, and thus relieve a lifetime burden of asthma in this high-risk urban children.

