2.1 Primary Objective

The primary objective of the continuation of URECA to age 17 is to determine the wheezing, asthma and atopy phenotypes in minority children growing up in poor urban neighborhoods as they develop from birth through adolescence.

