10.4 Analysis Plan

10.4.1 Primary Analysis of Primary Objective

The purpose of the primary analysis in the fourth phase of URECA will be to identify wheezing and asthma phenotypes in the children through the age of 17 years. Furthermore, we will identify risk factors for the asthma phenotypes related to environmental exposures, immune responses and biomarkers, weight and fitness status, and airway and environmental microbiota.

Using the extensively and longitudinally characterized URECA cohort, we will:

1. Categorize URECA subjects into already described early life patterns of wheezing (Tucson Children's Respiratory Study, Avon Longitudinal Study of Parents and Children, Prevention and Incidence of Asthma and Mite Allergy) and development of atopic disorders (Manchester) to determine if these patterns are indeed observed among inner-city American children.
2. Using longitudinal data obtained from the URECA cohort through the age of 17 years, we will perform a cluster analysis to identify patterns of wheezing, allergic sensitization and lung function over time. In URECA the comprehensive longitudinal measurements within a child allow the application of techniques such as latent class analysis where periods have the greatest impact on the development and maintenance of asthma through the teen years. In particular, symptoms, exacerbations, allergy, immunologic measures, BMI, fitness, psychosocial factors and objective measurements of lung function, spirometry, eNO and IOS will define clusters of asthma phenotypes based on a combination of these variables. We will consider latent class analysis and other clustering techniques to identify phenotypes in URECA V.

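### Section 10.4.3 puts demographics into the distance that forms the phenotypes, unlike the variable lists elsewhere, and then uses them to predict the same phenotypes

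*Protocol*

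**What the plan says.** Section 10.4.3 first fits latent class mixed models to each longitudinal variable. It then builds one Gower distance from two sources. The first is "Variables characterizing the trajectory clusters (e.g. symptoms, allergic sensitization, lung function and BMI" and so on. The second is worded as "other relevant predictors (including demographics) will be used to represent subjects in a Gower distance matrix, which can handle mixed data types". The only screen on the inputs is this: "These variables will be evaluated for collinearity and variable sets that are highly collinear will be represented by a constituent variable". The section then states: "Children will be clustered to identify distinct phenotypes selected using four criteria". Those criteria are a within-cluster sum of squares, average silhouette width, the Dunn index and a within-to-between ratio. No variable weights are given.

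Two other places say what forms the clusters. Section 10.4.1 lists symptoms, exacerbations, allergy, immunologic measures, BMI, fitness and psychosocial factors, and ends with "objective measurements of lung function, spirometry, eNO and IOS will define clusters of asthma phenotypes based on a combination of these variables". Aim 3a in section 1.2 speaks of "using advanced clustering techniques to identify respiratory and asthma phenotypes from longitudinal data, including upper and lower airway symptoms", followed by sensitization, lung function, BMI and psychosocial factors. Neither list contains demographics.

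Later in 10.4.3, the models that predict these phenotypes from early-life data are described as follows: "The candidate predictor variables for these models will include (i) demographics". The objective in section 2.1 is to "determine the wheezing, asthma and atopy phenotypes in minority children growing up in poor urban neighborhoods".

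**The concern.** A phenotype of wheeze, asthma or atopy should be formed from the course of disease. If demographics help to form it, two children with the same course can be separated because they differ in sex or race.

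An unweighted Gower distance makes this more likely than it looks. A categorical variable contributes 0 or 1 to each pair. A numeric variable is divided by its full range, so it usually contributes much less.

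Two consequences follow. First, demographics are both an ingredient of the phenotype and a candidate predictor of it, so an association can arise by construction. Second, the endotype and biomarker models take the clusters as their outcome. Methylation or expression patterns linked to sex or ancestry could then be reported as asthma biology.

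**Working it through.** The protocol gives no figure to reproduce here. The check has three parts.

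**1. Share of the distance.** Assumptions: demographics means sex and race (section 10.4.2.1 names race and gender as possible adjustments), all variables have equal weight, and sex is 50:50.

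- Sex: 1 - (0.5² + 0.5²) = 0.50.
- Race/ethnicity, from the Total row of Table 2 (21, 70, 7 and 3%, which sum to 101% by rounding, so each is divided by 1.01): 1 - (0.208² + 0.693² + 0.069² + 0.030²) = 0.47.
- Numeric variable, normal: mean absolute difference 1.128 SD over a range of about 6 SD at n = 442 (section 10.5), about 0.19. If uniform: 0.33.
- Class label with k equally frequent classes: 1 - 1/k, which is 0.50, 0.67 and 0.75 for k = 2, 3 and 4.

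Share of sex plus race = 0.97 / (0.97 + m × d), where m is the number of disease variables and d the mean contribution of each. Section 10.4.3 names four domains as examples.

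- m = 4, class labels: 0.97 / (0.97 + 2.00) = 33% for two classes; 0.97 / (0.97 + 3.00) = 24% for four classes.
- m = 4, numeric: 0.97 / (0.97 + 1.33) = 42% if uniform; 0.97 / (0.97 + 0.75) = 56% if normal.
- m = 8: 14-20% for class labels and 27-39% for numeric variables.

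**2. Effect on the clusters.** Simulation with n = 442, five true disease groups, k-medoids and equal weights; sex 50:50 and race as in Table 2, both independent of disease. The measure is the adjusted Rand index (ARI) with the true groups.

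| Disease inputs | Without demographics | With sex and race |
|---|---|---|
| Ten class labels | 0.97 | 0.91 |
| Four class labels | 0.79 | 0.70 |
| Two numeric, two labels | 0.63 | 0.45 |
| Ten numeric | 0.98 | 0.48 |
| Four numeric | 0.72 | 0.08 |

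A second simulation varied how well the groups separate (30 replicates per setting, k = 5):

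- Four numeric inputs, group levels spaced 3, 2 or 1 SD: ARI fell from 0.88 to 0.15, 0.63 to 0.08 and 0.21 to 0.04. ARI with sex rose from 0 to 0.44-0.48.
- Four three-level labels, kept with probability 0.90, 0.75 or 0.60 and otherwise redrawn at random: 0.78 to 0.67, 0.60 to 0.49 and 0.36 to 0.26. ARI with sex was 0.08-0.15.
- Eight labels, kept with probability 0.75: 0.87 to 0.83.

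**3. Whether the plan's own safeguards help.** The collinearity screen removes a variable only if it duplicates others, so it would not normally remove sex or race. The four selection criteria measure compactness and separation, not clinical meaning. Average silhouette width was computed with sex and race in the matrix and four disease variables. With numeric inputs the true disease partition scored 0.08-0.13 and a plain split by sex 0.42-0.44. With three-level labels, disease won when labels were clean (0.43 against 0.27) and lost when they were noisier (0.23 against 0.26; 0.11 against 0.25).

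**The case against.** The strongest reply is that section 10.4.3 describes two stages, and its natural reading is that trajectory-class labels, at least in part, enter the Gower matrix. The four domains are only examples, and section 10.4.1 names about ten. With ten labels, a separate run of 20 replicates lost almost nothing (0.91 to 0.89), and six labels plus four numeric inputs went from 0.88 to 0.80. Ten purely numeric inputs went from 0.85 to 0.19, but the protocol does not say that all inputs are numeric. Coding and weights may be set in an analysis plan that is not shown. This stands as a limit on the size of the harm. It does not remove the point, because the protocol itself fixes demographics as an input.

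A reader might infer that the phenotypes will simply be sex-by-race groups. One run with four numeric inputs does give that picture (ARI 0.74 to 0.06, with clusters 99% single-sex). It is the all-numeric worst case, not an estimate for this plan. Nor do the documents show that the later models will describe sex or ancestry instead of asthma. That step was not simulated and is only possible. Study site is not a demographic variable and is not named, so nothing here rests on it.

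A reader might also infer that the primary analysis is defective. The sentence stands under exploratory endpoints, while section 10.4.1 has its own list without demographics and leaves the technique open. What remains is ambiguity: 10.4.3 presents itself as the general approach to finding phenotypes, and section 10.2.1 makes phenotypes the primary endpoint.

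Finally, 10.4.3 says the approach resembles that used at 7 and 10 years. The protocol does not show whether demographics entered those distances, so this settles nothing either way.

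**Conclusion.** The point holds as a should-fix for the phenotype, endotype and biomarker analyses of section 10.4.3. It reaches the primary phenotypes only if the 10.4.3 approach is applied there.

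The text is explicit that demographics enter the distance. That does not match the cluster-defining lists in sections 10.4.1 and 1.2, and it makes the later use of demographics as predictors partly circular. These findings need no simulation.

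The size is uncertain: slight with many class labels, moderate with four labels or mixed inputs, and severe when all disease inputs are numeric. This range rests on reading demographics as sex and race, equal weights, a 50:50 sex ratio, five true groups, and independence of sex and race from disease. If sex or race does shape the course of disease, clusters built from disease variables alone can show it. Clusters that already contain sex or race cannot test it cleanly.

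**What to change.** In section 10.4.3, delete from the Gower sentence the clause that adds further predictors and demographics, so that the distance uses only the longitudinal disease variables, in line with sections 10.4.1 and 1.2. Use demographics afterwards, to describe the clusters and as covariates in the endotype and biomarker models. If there is a reason to see their influence on the clustering, add it as a labelled sensitivity analysis with the demographic variables and weights stated.

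The cost is one sentence and no new data. It should be done before clustering, because the later models inherit the clusters.
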